Part 1 of the study will commence with an accelerated dose escalation schedule and enrol 1 patient into a cohort with follow up for adverse events (AEs) and DLT during Cycle 1. The CRC will meet as soon as possible once the final study visit in Cycle 1 has taken place in each cohort to review patient safety data to the end of Cycle 1. Where there are no safety concerns, a 100% dose escalation step will be permitted for the next cohort. Where the CRC suspects that drug-related events have occurred that could progress to DLT upon further dose escalation e.g. clinically significant NCI (National Cancer Institute) CTCAE (Common Terminology Criteria for Adverse Events) Grade 2 events considered to be related to ALM201, they will confirm that future cohorts must enrol at least 3 patients in order to more thoroughly evaluate potential drug-related adverse events. The CRC may also advise that the current dose level under evaluation be expanded to 3 patients prior to further dose escalation in order to help inform the next dose escalation step. Dose escalation of 3-patient cohorts will proceed according to the scheme presented in [Section 4.2](#). Note that there will always be stagger of at least 1 week between dosing the first and subsequent patients in a new dose cohort. The CRC may request there be a further or prolonged stagger introduced during the trial, depending on the nature of adverse events observed to date.

Dose Limiting Toxicity

The CRC will agree on the next appropriate dose escalation step for each cohort primarily based on DLT evaluation during Cycle 1 of the current cohort. Only events occurring during the first cycle of treatment will be considered for DLT determination; however, there will be on-going evaluation of AEs in subsequent treatment cycles during the cohort review process. Clinically significant events thought to be potentially related to ALM201, or trends in adverse events seen in subsequent cycles will be taken into account when considering future dose escalation steps and dose administration schedules.

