Upon occurrence of the first DLT in any cohort, additional patients will be added to that cohort so that up to a total of 6 can be evaluated. Once expansion to a 6-patient cohort has been recommended due to the identification of a DLT, escalation to the next 3-patient cohort will only occur when all patients in the expanded cohort have completed their first cycle of ALM201 and no more than 1 DLT has occurred. If 2 or more DLTs occur in an expanded cohort, DLT is established and the next lower dose level will be declared the MTD.

The highest dose where ≤ 1 DLT is seen in 3 or 6 patients will be termed the MTD. Note that intermediate dose levels may be explored below the dose level where ≥ 2 DLTs were seen, in order to identify the maximum dose which may be adequately tolerated. The CRC may also specify a recruitment stagger to be followed during cohort expansion for DLT evaluation depending on the nature of the DLT and the considered risk to patients.

In the case where an MTD is not established, the maximum feasible single dose which may be administered will be dictated by the formulation of ALM201 and the maximum volume for SC administration i.e. 3 x 1 mL injections, which will administer a dose of 300 mg ALM201 ([Section 6](#)). Should this dose be reached without the need to de-escalate due to DLT, it will be termed the MFD.

Based on the review of PD data in conjunction with on-going safety and PK data, the CRC may also identify a BAD for further exploration in Part 2 of the study.

Safety evaluations will be conducted weekly during each treatment cycle, with DLT assessed during Cycle 1 only. All events and suspected DLTs will be graded according to the CTCAE v4.03.

A DLT is defined as a Grade 3 or 4 AE that, in the opinion of the CRC, is likely to be related to ALM201 and represents a clinically significant hazard to the subject. Qualifying DLT events must be considered to be clinically relevant e.g. in duration, apparent reversibility, required management, and upon consideration of the patient's medical history and/or concomitant medications. DLT events must also be evaluated in terms of what is considered to be an appropriate next escalation step: in the case where the CRC agree that an escalation step of approximately 33% or lower is merited, the toxicity of concern should be declared a DLT.

Examples of exceptions that will be considered by the CRC are as follows:

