- Grade 3 or 4 laboratory abnormalities, which resolve spontaneously or can be corrected with appropriate treatment (such as electrolytes) e.g. an event returns to baseline or to Grade 1 or less prior to the next administration);
- Symptomatic adverse events, such as nausea, vomiting and diarrhea, if they can be reduced to less than Grade 3 with standard supportive measures, such as anti-emetics and anti-diarrhoeals within 72 hours.

In order to be evaluable for DLT assessment, a patient must have received at least 80% of their scheduled doses (e.g. 12 of the 15), unless this lack of compliance is due to ALM201-related toxicity. DLT events must therefore be considered in terms of inability to administer the planned Cycle 1 dose administration schedule, and in such cases a dose delay of more than 14 days due to a toxicity event considered related to ALM201 will be considered to be a DLT ([Section 4.4.1](#)).

Part 1: Dose Escalation

In the absence of DLT or suggestion of ALM201-related adverse events which would lead to more cautious dose escalation, the following table presents a hypothesised dose escalation plan:

Cohort	Escalation Step	Dose level
1 (Starting Dose)	-	10 mg
2	(2X starting dose)	20 mg
3	(4X starting dose)	40 mg
4	(8X starting dose)	80 mg
5	(16X starting dose)	160 mg
6 (MFD)	(30X starting dose)	300 mg

The dose may be doubled in sequential cohorts where the CRC consider it appropriate to do so, based on on-going evaluation of DLTs and adverse event data. Dose escalation decisions will also take available PK and pharmacodynamic (PD) data into consideration.

In the case where a potentially significant toxicity occurs, or a trend in toxicities is seen, considered to be related to treatment with ALM201 and potentially a precursor to a clinically significant toxicity event, subsequent dose escalation steps will be more conservative and will not exceed 50% of the previous dose. This restriction may be reversed where there is no suggestion of potentially clinical significant toxicity in subsequent cohort(s). In the case where a single DLT event is confirmed in an expanded cohort, the next dose escalation step will not exceed 33% of the previous dose. However, where there are no further events seen in the next cohort; the CRC may allow future dose escalation steps of up to 50%.

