Note that the CRC may also recommend that an MTD, MFD or BAD be assessed in a cohort of 6 patients in Part 1 where only 3 patients have received this dose level to date, prior to recommending the enrolment of an enrichment cohort to receive this dose level in Part 2.

Cohort Review Committee

All dose escalation decisions will be made by a CRC who shall convene to review all available AE, PK, PD and relevant patient data ([Section 8.1](#)). Patients in Part 1 will be eligible for DLT evaluation if they have received 80% e.g. 12 of their 15 scheduled doses, during Cycle 1. The CRC will be composed of the trial investigators, a patient representative, sponsor representative(s) and the study Medical Monitor. Additional experts may be invited to support the review of the data as required e.g. a pharmacokineticist. The Contract Research Organisation (CRO) responsible for managing and monitoring the trial will also support the preparation and conduct of the CRC meetings and may attend such meetings. All data reviewed, CRC discussions and agreed dose escalation recommendations will be minuted. The composition of the CRC and the data review processes to be followed by the committee will be fully described in a CRC Charter.

Based on on-going safety, PK and PD data evaluation, the CRC may also recommend dose de-escalation steps or adjustments in the dose administration schedule of ALM201. Upon review of available safety, PK and PD data, the CRC may recommend that an alternative dose administration schedule of ALM201 be explored. Less intense dose administration schedules will be permitted as long as the unit dose does not exceed the next permitted escalation step. Given the starting dose administration schedule is week-day dosing i.e. D1-5, D8-12, D15-19, on a 21 day cycle, a more dose intense dosing schedule is unlikely. However, should the CRC consider this reasonable to explore, the same dose escalation rules will apply and pharmacokinetic modelling, in conjunction with the safety data obtained to date, will be used to inform the appropriate dose level for a more dose intense dose schedule.

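### The synopsis DLT definition stops at Grade 4, so a likely related Cycle 1 death is not expressly a DLT and is counted only through committee judgement under two other clauses

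*Protocol*

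**What the plan says.** The definition is in the Protocol Synopsis under Dose Limiting Toxicity: "A DLT is defined as a Grade 3 or 4 AE that, in the opinion of the CRC, is likely to be related to ALM201". It adds that the event must be a clinically significant hazard. Events are graded by CTCAE v4.03. No DLT wording in the supplied text mentions Grade 5 or death.

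Two other provisions can make an event a DLT, and neither has a grade limit:

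- **Step-size clause**, in the same paragraph. If the CRC agrees that "an escalation step of approximately 33% or lower is merited, the toxicity of concern should be declared a DLT".
- **Dosing-inability wording**, in the evaluability paragraph that follows. DLTs are to be considered in terms of whether the Cycle 1 schedule could be given, and a related delay of more than 14 days is a DLT.

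The DLT count then drives the rules:

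- **Expansion:** "Upon occurrence of the first DLT in any cohort, additional patients will be added to that cohort", towards six.
- **MTD:** "If 2 or more DLTs occur in an expanded cohort, DLT is established and the next lower dose level will be declared the MTD".
- **Step cap:** after a single DLT confirmed in an expanded cohort, the next step is capped at 33% (Part 1: Dose Escalation).

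Some safeguards do not need a DLT. In the accelerated phase, "The CRC may also advise that the current dose level under evaluation be expanded to 3 patients prior to further dose escalation". In addition, "the CRC may also recommend that an MTD, MFD or BAD be assessed in a cohort of 6 patients in Part 1". After a potentially significant related toxicity, "subsequent dose escalation steps will be more conservative and will not exceed 50% of the previous dose".

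SAP 4.7.1 lists a DLT table, tables of TEAEs of Grade 3 and above, and a fatal TEAE table. It does not redefine a DLT.

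**The concern.** CTCAE reserves Grade 5 for death. A definition that names Grades 3 and 4 and stops there literally leaves out the worst related outcome, while including lesser ones. Mandatory expansion, the 33% cap, the two-DLT rule and the MTD all use the same count. An event left out of the count therefore moves those decisions from rule to discretion.

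The gap lies only in the grade range. Every DLT in this study needs a CRC opinion on relatedness, and that is not at issue.

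**Working it through.** The plan states no figure that depends on this point, so there is nothing to reproduce. The check is a reading of each route to a DLT, followed by the dose arithmetic.

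**Step 1. Does any route expressly cover a related Cycle 1 death?**

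| Route | Grade limit | Names death? | What it needs |
|---|---|---|---|
| Definition sentence | Grade 3 or 4 | No | CRC view on relatedness and hazard |
| Step-size clause | None | No | CRC agreement that a step of about 33% or less is merited |
| Dosing-inability wording | None | No | CRC view that the schedule could not be given; the express trigger is a delay of more than 14 days |

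The step-size clause would probably catch a death, because stopping or de-escalating is naturally read as a step below 33%. The dosing-inability wording plausibly fits too, although a death is not literally a delay. SAP 3.6.2 shows that dosing lost through related toxicity is not automatically a DLT: it provides for such patients whose toxicity is not finally so classed and leaves their evaluability to case-by-case review. Both routes therefore rest on judgement.

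**Step 2. What follows if neither route is used?** Take a three-patient cohort with one likely related death and no Grade 3 or 4 DLT.

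- Death counted: 1/3. Expansion towards six is mandatory. If no second DLT occurs, the next step is capped at 33%.
- Death not counted: 0/3. Expansion is at the CRC's discretion. The cap is 50%, provided the significant-toxicity rule is applied. That rule is worded for events that may foreshadow something worse; I take it to apply to a death all the more.

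**Step 3. Dose arithmetic.** Percentages are read as increments, so the maximum next dose is the current dose × (1 + cap). The current doses come from the hypothesised escalation table.

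- From 80 mg: 80 × 1.50 = 120 mg versus 80 × 1.33 = 106.4 mg, a difference of 13.6 mg.
- From 160 mg: 160 × 1.50 = 240 mg versus 160 × 1.33 = 212.8 mg, a difference of 27.2 mg.
- Ratio in both cases: 1.50 / 1.33 = 1.128, so 12.8% higher.

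**Step 4. How far can this reach?** If the CRC thinks a step of about 33% or less is merited, the step-size clause makes the event a DLT and the gap closes. The difference in Step 3 therefore arises only if the CRC judges a death likely related and still finds a step above 33% merited.

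**The case against.** The strongest reply is that no CRC would leave a related death uncounted. All escalation decisions are the CRC's, made on all available data, and it may recommend de-escalation. The listed exceptions cover correctable laboratory values and manageable symptoms; none would excuse a death. Only the synopsis is supplied, and Sections 4.2.1 and 4.4.1 and the CRC Charter may already include Grade 5. SAP section 1 says the study was halted at the end of Part 1, so a protocol edit changes no dosing decision in it. A fatal TEAE would still appear in the fatal and Grade 3-and-above tables.

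All of this stands and limits the impact. It does not change what the definition sentence says.

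Three stronger readings are tempting, and the documents do not support them:

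- **That the step-size clause is the only way in.** The dosing-inability wording is a second route without a grade limit.
- **That related deaths would go uncounted.** The text leaves them to judgement; it does not exclude them from that judgement.
- **That an expanded cohort with one Grade 3 or 4 DLT and one related death would count 1/6 instead of 2/6, and so could escalate.** Escalation from an expanded cohort also requires that all its patients have "completed their first cycle of ALM201 and no more than 1 DLT has occurred". Read just as literally, a patient who died in Cycle 1 has not met the first part. Moreover, the first DLT already caps the next step at 33%, and finding only such a step merited would naturally engage the step-size clause and make the death the second DLT.

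**Conclusion.** The defect holds as a gap in wording. The synopsis definition does not expressly make a likely related Cycle 1 death a DLT, and the two clauses that could do so depend on CRC judgement and do not name death. If neither is used, a three-patient cohort reads 0/3 instead of 1/3, expansion becomes optional, and the next dose may be 12.8% higher than the 33% cap allows.

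This rests on three assumptions: a literal reading of the grade range, percentages read as increments, and the 50% limit being applied. The CRC would very probably act, so the severity is minor. Confidence is medium, because the fuller protocol sections and the Charter cannot be checked. The supplied documents do not report whether any such death occurred. With Part 1 over, the live consequence is how events are classified in the DLT table.

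**What to change.** In the synopsis definition, replace *Grade 3 or 4 AE* with *Grade 3 or higher AE*. Make the same change in Section 4.2.1 and the CRC Charter if they share the wording. Relatedness stays with the CRC. No new evaluability rule is needed: once the death is a DLT, the existing exemption for doses missed through ALM201-related toxicity covers that patient.

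For the final Part 1 report, add one line to SAP 4.7.1 confirming that the DLT table includes any Cycle 1 Grade 5 event that the CRC judged likely related to ALM201. The line should follow the CRC's recorded judgement, because SAP 4.7.1 defines relatedness by the investigator and names no CRC causality variable.

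The cost is a few words in the protocol, one line in the SAP, and a check of the CRC minutes, which the synopsis requires to be kept. Other tables are unchanged, and so is the DLT table if there was no such event.

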12. Any evidence of severe or uncontrolled systemic conditions or any other issues which make it undesirable for the patient to participate in the study or which could jeopardize compliance with the protocol.

Route of Administration, Dose Schedule and Duration:

ALM201 administered as a SC injection with a maximum administration volume of 1.0 mL per injection. Each 1 ml injection will contain 100 mg ALM201. A maximum of 3 x 1.0 mL injections may be given for any single dose, therefore the MFD will be 300 mg. The starting dose level of ALM201 is 10 mg given on Days 1-5, 8-12 and 15-19 of a 21-day cycle. The SC injection may be given in the abdomen, leg or arm following local administration guidelines including the use of premedication as required for local injection site reactions. The dose levels assessed in this study i.e. the dose and dosing administration schedule, may be adjusted following the study dose escalation rules, based on review of on-going evaluation of safety, PK and PD data generated during the study.

Statistical Methods:

There will be no formal statistical analysis in the dose-escalation phase this study. Results will be listed and summarised using descriptive statistics. In Part 2, response rate will be assessed and summarised and an exact 95% confidence interval (CI) calculated. Analyses will be performed on the whole population plus those who have and have not been previously exposed to anti-angiogenics and those who have and not been exposed to tubulin-targeting agents before entry to this trial.

SCHEDULE OF STUDY ASSESSMENTS

(i) Schedule of Assessments for Starting Dose Administration Schedule: Day 1-5, 8-12 and 15-19 of a 21-day dosing schedule

	Screening	Cycle 1 (21 d cycle)							Cycle 2 – 4 (21 d cycle)					Cycle 5 – 8 (21 d cycle)					Final Study Visit ¹¹	Long-term Follow Up							
		Day							Day					Day													
	-28 to 0	1	2	3-5	8	9-12	15	16-19	22/1 ¹⁰	2-5	8	9-12	15	16-19	22/1 ¹⁰	2-5	8	9-12			15	16-19	22/1 ¹⁰				
Informed consent	X																										
Demographics	X																										
Medical history	X																										
Inclusion/exclusion	X																										
ECOG PS	X								X						X							X		X			
Physical examination ¹	X	X			X		X		X		X		X		X		X		X		X		X		X		
Vital signs ²	X	X	X	X	X	X	X	X	X		X		X		X		X		X		X		X		X		
ECG (resting 12-lead) ³	X	X							X						X						X						
Clinical chemistry*	X	X			X		X		X		X		X		X		X		X		X		X		X		
Echocardiogram	X																										
Haematology	X	X			X		X		X		X		X		X		X		X		X		X		X		
Coagulation	X	X			X		X		X		X		X		X		X		X		X		X		X		
Urinalysis*	X	X							X						X						X						
Tumour assessment (radiological) ⁴	X								X ⁴						X ⁴						X ⁴		X ⁴		X ⁴		
Tumour assessment (serum marker) ⁴	X	X							X						X						X ⁴		X ⁴		X ⁴		
Immunogenicity assessment		X							X						X						X		X				
Biomarker/PD assessment (biopsy) ⁵	X	X - up to 2 post-treatment samples																									
Biomarker/PD assessment (blood sample) ⁶	X	X - up to 12 post-treatment samples																									
Biomarker/PD assessment (ascites) ⁷	(X)	(X - up to 5 post-treatment samples)																									
Biomarker (germ-line DNA) testing ⁸		(X)																									
Adverse events		X	X	X	X	X	X	X	X		X		X		X		X		X		X		X		X		
Concomitant medication	X	X	X	X	X	X	X	X	X		X		X		X		X		X		X		X		X		
ALM201 administration		X	X	X	X	X	X	X	X	X	X	X	X	X	X	X	X	X	X	X	X	X	X	X	X	X	
Pharmacokinetics ⁹		X	X	X				X	X					X	X					X	(X)						
Long-term follow up ¹²																										X	

Footnotes - General

- Assessments made on Day 1 of each cycle are to be conducted prior to ALM201 administration, unless specified otherwise.
- Additional assessments may be conducted as clinically indicated.
- (X) denotes an assessment not applicable to all patients.
- A tolerance of +/-1 day will be permitted for all study visits and a tolerance of -1 day for all assessments relative to the study visit, unless specified otherwise.
- * ***female patients, if fertile, will require a serum pregnancy test at Screening and urine pregnancy on Day 1 of each cycle***

Assessment Specific

1. Patient's height will be recorded at Screening. A full physical examination is required at Screening and prior to Day 1 of each cycle; Symptom-directed physical examination is acceptable at other time-points. Weight will be recorded at Screening and on Day 1 of each cycle.
2. On each hospital administration day, vital signs (heart rate, BP, temperature and respiration rate) will be assessed pre-dose and up to 1 hour after the ALM201 injection. Patient status will be monitored during ALM201 administration and repeat vital signs will be taken if needed.
3. On Cycle 1, Day 1 a resting 12-lead ECG will be conducted pre-dose and 30 mins (+/- 15 mins) after ALM201 injection. On Day 1 of all other cycles, a resting 12-lead ECG will be conducted pre-dose only.
4. CT or MRI performed at Screening and up to 7 days prior to start of Cycle 3, 5, 7 and at the end of Cycle 8. Note that where there is a rationale for assessment of bone lesions, these assessments will be performed as part of the CT or MRI assessment and will not require additional radiological bone scan assessment.

Other informative markers e.g. CA-125, PSA, photographs of melanoma skin lesions, may be taken as appropriate on Day 1 of each cycle.

Additional scans may be performed to confirm a Complete Response (CR) or Partial Response (PR) or disease progression (PD) as per appropriate response assessment guidelines. Any requirement for confirmatory scans will typically be performed at the next protocolled assessment time point. Other assessments e.g. whole body MRI or PET, are not protocol mandated, but may be performed as clinically indicated and at request of Investigator.

5. Patients with available archived biopsy samples will consent to provide these for biomarker/PD evaluation. The study will encourage taking fresh biopsies for biomarker/PD evaluation at Screening and post-treatment upon tumour response and/or at the point of disease progression. Although optional, every effort should be made to collect fresh pre and post-dose biopsy samples from patients – particularly in Part 2 - and imaging techniques may be used to facilitate this process.
6. Assessment of biomarker/PD activity from blood samples taken to obtain serum, plasma, PBMC or CTCs, may be conducted in all patients between Screening, Cycle 6 and Final Study Visit, with no more than 2 samples taken on any study day, 4 in any treatment cycle, and 13 in total during 6 cycles (including Screening and Final Study Visit). Time-points may vary depending on the assay and method of analysis.
7. Assessment of biomarker/PD activity in ascites may be conducted in relevant patients who are undergoing draining of ascites as part of their standard of care. This procedure would normally be performed under ultrasound marking. It is estimated that the study may obtain up to 6 samples over 8 cycles (including Screening and Final Study Visit). Actual time-points may vary within each cycle.
8. Consenting patients will have a 10 mL blood sample taken for preparation of a germ-line DNA sample at Screening (recommended time-point only).

9. Patients will have a 12-hour urine collection on Cycle 1, Day 1 for urine PK analysis.

Patients will have PK blood sampling conducted at Cycle 1 at the following sample times. Three PK profiles may be taken: each will not exceed up to 12 samples taken out to 24 hours post ALM201 injection. The CRC may advise on adjusted time-points. The maximum number of PK samples to be collected during any Cycle 1 dose schedule will not exceed 40. The actual time for each blood draw must be accurately recorded. Initial sampling time points are:

Cycle 1, Day 1:

All doses (except 300mg): Predose, then 15 mins (+/- 5 mins), 45 mins (+/- 5 mins), 1.5 hr (+/- 10 mins), 2 hr (+/- 10 mins), 3 hr (+/- 10 mins), 4 hr (+/- 10 mins), 5 hr (+/- 10 mins), 6 hr (+/- 10 mins), 22 hr (+/- 1hr).

Doses of 300 mg: Predose, then 15 mins (+/- 5 mins), 45 mins (+/- 5 mins), 1.5 hr (+/- 10 mins), 2 hr (+/- 10 mins), 3 hr (+/- 10 mins), 4 hr (+/- 10 mins), 5 hr (+/- 10 mins), 6 hr (+/- 10 mins), 7 hr (+/- 10 mins), 8 hr (+/- 10 mins), 22 hr (+/- 1hr).

Cycle 1, Day 3 & 18:

All doses (except 300mg): Predose, then 30mins (+/- 5 mins), 60 mins (+/- 5 mins), 1.5 hr (+/- 10 mins), 2 hr (+/- 10 mins), 3.5 hr (+/- 10 mins), 5 hr (+/- 10 mins).

Doses of 300 mg: Predose, then 30 mins (+/- 5 mins), 60 mins (+/- 5 mins), 1.5 hr (+/- 10 mins), 2 hr (+/- 10 mins), 4.5 hr (+/- 10 mins), 7 hr (+/- 1 hr).

Cycles 2, 4, 6 & 8, Day 18:

All doses (except 300mg): Predose, then 30mins (+/- 5 mins), 60 mins (+/- 5 mins), 1.5 hr (+/- 10 mins), 2 hr (+/- 10 mins), 3.5 hr (+/- 10 mins), 5 hr (+/- 10 mins).

Doses of 300 mg: Predose, then 30 mins (+/- 5 mins), 60 mins (+/- 5 mins), 1.5 hr (+/- 10 mins), 2 hr (+/- 10 mins), 4.5 hr (+/- 10 mins), 7 hr (+/- 1 hr).

A single pre-dose sample will also be taken on Cycles 2-8 on Day 1.

10. Day 22 of Cycle 1, 2, 3, 4, 5, 6 and 7 is Day 1 of Cycle 2, 3, 4, 5, 6, 7 and 8.
11. The Final Study Visit should be performed 30 +/-3 days after the last dose of ALM201 to enable a final safety assessment.
12. Those patients who do not have disease progression at the Final Study Visit will be contacted every 8 weeks for up to 2 years (approximately) to check their status and commencement of their next anticancer treatment.

(ii) Schedule of Study Assessments for Alternative Dose Schedules

	Screening	Cycle 1				Cycle 2 – 4			Cycle 5 – 8				Final Study Visit ¹¹	Long-term Follow Up
		Day				Day			Day					
	-28 to 0	1	2	Other dosing days	Weekly clinic visits	22/1 ¹⁰	Other dosing days	Weekly contact	22/1 ¹⁰	Other dosing days	Weekly contact	22/1 ¹⁰		
Informed consent	X													
Demographics	X													
Medical history	X													
Inclusion/exclusion	X													
ECOG PS	X					X			X			X	X	
Physical examination ¹	X	X			X	X		X	X		X	X	X	
Vital signs ²	X	X			X	X		X	X		X	X	X	
ECG (resting 12-lead) ³	X	X				X			X			X		
Echocardiogram	X													
Clinical chemistry*	X	X			X	X		X	X		X	X	X	
Haematology	X	X			X	X		X	X		X	X	X	
Coagulation	X	X			X	X		X	X		X	X		
Urinalysis*	X	X				X			X			X		
Tumour assessment (radiological) ⁴	X					X ⁴			X ⁴			X ⁴	X ⁴	
Tumour assessment (serum marker) ⁴	X	X				X			X			X ⁴	X ⁴	
Immunogenicity assessment		X				X			X			X		
Biomarker/PD assessment (biopsy) ⁵	X	X – up to 2 post-treatment samples												
Biomarker/PD assessment (blood sample) ⁶	X	X - up to 12 post-treatment samples												
Biomarker/PD assessment (ascites) ⁷	(X)	(X – up to 5 post-treatment samples)												
Biomarker (germ-line DNA) testing ⁸		(X)												
Adverse events		X	X	X	X	X		X	X		X	X	X	
Concomitant medication	X	X	X	X	X	X		X	X		X	X	X	
ALM201 administration		X (D1 + additional doses following dosing Schedule)				X (as per dosing schedule)								
Pharmacokinetics ⁹		X	X	X		X	X		X	X		(X)		
Long-term follow up ¹²														X

Footnotes - General

- Assessments made on Day 1 of each cycle are to be conducted prior to ALM201 administration, unless specified otherwise.
- Additional assessments may be conducted as clinically indicated.
- (X) denotes an assessment not applicable to all patients.
- A tolerance of +/-1 day will be permitted for all study visits and a tolerance of -1 day for all assessments relative to the study visit, unless specified otherwise.
- * ***female patients, if fertile, will require a serum pregnancy test at Screening and urine pregnancy on Day 1 of each cycle***

Assessment Specific

1. Patient's height will be recorded at Screening. A full physical examination is required at Screening and prior to Day 1 of each cycle; Symptom-directed physical examination is acceptable at other time-points. Weight will be recorded at Screening and on Day 1 of each cycle.
2. On each hospital administration day, vital signs (heart rate, BP, temperature and respiration rate) will be assessed pre-dose and up to 1 hour after the ALM201 injection. Patient status will be monitored during ALM201 administration and repeat vital signs will be taken if needed.
3. On Cycle 1, Day 1 a resting 12-lead ECG will be conducted pre-dose and 30 mins (+/- 15 mins) after ALM201 injection. On Day 1 of all other cycles, a resting 12-lead ECG will be conducted pre-dose only.
4. CT or MRI performed at Screening and up to 7 days prior to start of Cycle 3, 5, 7 and at the end of Cycle 8. Note that where there is a rationale for assessment of bone lesions, these assessments will be performed as part of the CT or MRI assessment and will not require additional radiological bone scan assessment.

Other informative markers e.g. CA-125, PSA, photographs of melanoma skin lesions, may be taken as appropriate on Day 1 of each cycle.

Additional scans may be performed to confirm a Complete Response (CR) or Partial Response (PR) or disease progression (PD) as per appropriate response assessment guidelines. Any requirement for confirmatory scans will typically be performed at the next protocolled assessment time point. Other assessments e.g. whole body MRI or PET, are not protocol mandated, but may be performed as clinically indicated and at request of Investigator.

5. Patients with available archived biopsy samples will consent to provide these for biomarker/PD evaluation. The study will encourage taking fresh biopsies for biomarker/PD evaluation at Screening and post-treatment upon tumour response and/or at the point of disease progression. Although optional, every effort should be made to collect fresh pre and post-dose biopsy samples from patients – particularly in Part 2 - and imaging techniques may be used to facilitate this process.
6. Assessment of biomarker/PD activity from blood samples taken to obtain serum, plasma, PBMC or CTCs, may be conducted in all patients between Screening, Cycle 6 and Final Study Visit, with no more than 2 samples taken on any study day, 4 in any treatment cycle, and 13 in total during 6 cycles (including Screening and Final Study Visit). Time-points may vary depending on the assay and method of analysis.
7. Assessment of biomarker/PD activity in ascites may be conducted in relevant patients who are undergoing draining of ascites as part of their standard of care. This procedure would normally be performed under ultrasound marking. It is estimated that the study may obtain up to 6 samples over 8 cycles (including Screening and Final Study Visit). Actual time-points may vary within each cycle.
8. Consenting patients will have a 10 mL blood sample taken for preparation of a germ-line DNA sample at Screening (recommended time-point only).

9. Patients will have a 12-hour urine collection on Cycle 1, Day 1 for urine PK analysis.

Patients will have PK sampling conducted at Cycle 1 at the following sample times. Three PK profiles may be taken: each will not exceed up to 12 samples taken out to 24 hours post ALM201 injection. The CRC may advise on adjusted time-points. The maximum number of PK samples to be collected during any Cycle 1 dose schedule will not exceed 40. The actual time for each blood draw must be accurately recorded. Initial sampling time points are:

Cycle 1, Day 1:

All doses (except 300mg): Predose, then 15 mins (+/- 5 mins), 45 mins (+/- 5 mins), 1.5 hr (+/- 10 mins), 2 hr (+/- 10 mins), 3 hr (+/- 10 mins), 4 hr (+/- 10 mins) , 5 hr (+/- 10 mins) , 6 hr (+/- 10 mins), 22 hr (+/- 1hr).

Doses of 300 mg: Predose, then 15 mins (+/- 5 mins), 45 mins (+/- 5 mins), 1.5 hr (+/- 10 mins), 2 hr (+/- 10 mins), 3 hr (+/- 10 mins), 4 hr (+/- 10 mins), 5 hr (+/- 10 mins), 6 hr (+/- 10 mins), 7 hr (+/- 10 mins), 8 hr (+/- 10 mins), 22 hr (+/- 1hr).

Cycle 1, Day 3 & 18:

All doses (except 300mg): Predose, then 30mins (+/- 5 mins), 60 mins (+/- 5 mins), 1.5 hr (+/- 10 mins), 2 hr (+/- 10 mins), 3.5 hr (+/- 10 mins), 5 hr (+/- 10 mins).

Doses of 300 mg: Predose, then 30 mins (+/- 5 mins), 60 mins (+/- 5 mins), 1.5 hr (+/- 10 mins), 2 hr (+/- 10 mins), 4.5 hr (+/- 10 mins), 7 hr (+/- 1 hr).

Cycles 2, 4, 6 & 8, Day 18:

All doses (except 300mg): Predose, then 30mins (+/- 5 mins), 60 mins (+/- 5 mins), 1.5 hr (+/- 10 mins), 2 hr (+/- 10 mins), 3.5 hr (+/- 10 mins), 5 hr (+/- 10 mins).

Doses of 300 mg: Predose, then 30 mins (+/- 5 mins), 60 mins (+/- 5 mins), 1.5 hr (+/- 10 mins), 2 hr (+/- 10 mins), 4.5 hr (+/- 10 mins), 7 hr (+/- 1 hr).

A single pre-dose sample will also be taken on Cycles 2-8 on Day 1.

10. Day 22 of Cycle 1, 2, 3, 4, 5, 6 and 7 is Day 1 of Cycle 2, 3, 4, 5, 6, 7 and 8.
11. The Final Study Visit should be performed 30 +/-3 days after the last dose of ALM201 to enable a final safety assessment.
12. Those patients who do not have disease progression at the Final Study Visit will be contacted every 8 weeks for up to 2 years (approximately) to check their status and commencement of their next anticancer treatment.

(iii) Schedule of Assessments for Cycle 9 onwards

	Cycle 9 onwards			Final Study Visit ⁶	Long-term Follow Up
	Day 22/1 ⁵	Dosing days	Weekly contact		
ECOG PS	X			X	
Brief physical examination ¹	X			X	
Vital signs ²	X			X	
ECG (resting 12-lead)	X				
Clinical chemistry*	X			X	
Haematology	X			X	
Coagulation	X				
Urinalysis*	X				
Tumour assessment (radiological) ³	X ³			X ³	
Tumour assessment (serum marker) ³	X			X	
Immunogenicity	X			X	
Biomarker/PD assessment (biopsy) ⁴	X				
Adverse events	X		X	X	
Concomitant medication	X		X	X	
ALM201 administration		X			
Long-term follow up ⁷					X

Footnotes - General

- Assessments made on Day 1 of each cycle are to be conducted prior to ALM201 administration, unless specified otherwise.
 - Additional assessments may be conducted as clinically indicated.
 - (X) denotes an assessment not applicable to all patients.
 - A tolerance of +/-1 day will be permitted for all study visits and a tolerance of -1 day for all assessments relative to the study visit, unless specified otherwise.
- * ***female patients, if fertile, will require a serum pregnancy test at Screening and urine pregnancy on Day 1 of each cycle***

Assessment Specific

1. Symptom-directed physical examination. Weight will be recorded on Day 1 of each cycle.
2. On each hospital administration day, vital signs (heart rate, BP, temperature and respiration rate) will be assessed pre-dose and up to 1 hour after the ALM201 injection. Patient status will be monitored during ALM201 administration and repeat vital signs will be taken if needed.
3. CT or MRI performed at Screening and up to 7 days prior to start of every 4 cycles. Note that where there is a rationale for assessment of bone, these assessments will be performed as part of the CT assessment and not require additional radiological bone scan assessment.

Other informative markers e.g. CA-125, PSA, photographs of melanoma skin lesions, may be taken as appropriate on Day 1 of each cycle.

Additional scans may be performed to confirm a Complete Response (CR) or Partial Response (PR) or disease progression (PD) as per appropriate response assessment guidelines. Any requirement for confirmatory scans will typically be performed at the next protocolled assessment time point. Other assessments e.g. whole body MRI or PET, are not protocol mandated, but may be performed as clinically indicated and at request of Investigator.

4. A post-treatment biopsy should be taken where possible if the patient has disease progression.
5. Day 22 of Cycle 9, 10, 11, 12, etc is Day 1 of Cycle 10, 11, 12, 13, etc.
6. The Final Study Visit should be performed 30 +/-3 days after the last dose of ALM201 to enable a final safety assessment.
7. Those patients who do not have disease progression at the Final Study Visit will be contacted every 8 weeks for up to 2 years (approximately) to check their status and commencement of their next anticancer treatment.
